Grade 3 or 4 ^{a,b}	
First Occurrence:
 
 • For AEs present before the next dose of MEDI-551 is to be given, delay next dose of MEDI-551 for up to 7 days until resolution to ≤ Grade 1 or baseline, and resume at 50% of current dose level. • If next dose is delayed for > 7 days due to failure of toxicity to resolve to ≤ Grade 1 or baseline, permanently discontinue MEDI-551. • For Grade 3 infusion reaction, infusion must be stopped for up to 4 hours until the subject recovers. An additional dose of steroids will be given and the infusion may resume but the infusion rate must be decreased by 50% for remainder of infusion. For Grade 3 infusion reaction that does not respond to medical therapy (including interruption of infusion for ≤ 4 hours) or that occurs despite steroid prophylaxis, discontinue MEDI-551. • For any Grade 4 infusion or allergic reaction that necessitates the use of systemic pressor agents, permanently discontinue MEDI-551. 
Second Occurrence:
 
 • For AEs present before the next dose of MEDI-551 is to be given, permanently discontinue MEDI-551.
Hematologic Toxicity ^{c,d}	
Grade 1 or 2	None
Grade 3 ^{a,b}	
First Occurrence:
 
 • Delay dose by up to 7 days until resolution to ≤ Grade 2 and resume at current dose level. If subject does not recover to ≤ Grade 2 within that time, permanently discontinue MEDI-551. 
Second Occurrence:
 
 • Delay dose by up to 7 days until resolution to ≤ Grade 2 and decrease dose by 50%. If subject does not recover to ≤ Grade 2 within that time, permanently discontinue MEDI-551. 
Third Occurrence:
 
 • Permanently discontinue MEDI-551.
Grade 4 ^{a,b}	
First Occurrence:
 
 • Delay dose by up to 7 days until resolution to ≤ Grade 2 and decrease dose by 50%. If subject does not recover to ≤ Grade 2 within that time, permanently discontinue MEDI-551. 
Second Occurrence:
 
 • Permanently discontinue MEDI-551.

See Section 6.4.1 for additional details on dose interruption and study discontinuation criteria.

- ^a Except Grade 3 or 4 toxicities noted as exceptions to the Dose Limiting Toxicity (DLT) criteria (see Section 4.5.6).
- ^b Please note that for laboratory findings observed in the absence of clinical abnormality, repeat laboratory testing will be conducted to confirm significant laboratory findings before implementing dose modification.
- ^c For advanced B-cell malignancy dose escalation/expansion, hematologic abnormalities equal in severity to the subject's baseline and lymphopenia (any grade) do not require dose modification.
- ^d For subjects in Arms B, C, and D, lymphopenia or changes in lymphocyte counts will not be considered hematologic toxicities. Hematologic abnormalities equal in severity to the subject's baseline grade will not warrant dose modification unless they recur after normalization or improvement in the counts to ≤ Grade 2. Thereafter, hematologic abnormalities will require dose modification or cessation of dosing as indicated in

Table 4.5.2.1-2 MEDI-551 Dose Modifications for Nonhematologic and Hematologic Toxicity in Arms B, C, and D

Toxicity Grade	Dose Modification of MEDI-551
----------------	-------------------------------

this table.

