In the event of an IRR, the infusion of MEDI-551 may be decreased by 50% or interrupted until resolution of the event (up to 4 hours) and re-initiated at 50% of the initial rate until completion of the infusion. Acetaminophen and/or an antihistamine (eg, diphenhydramine) may be administered at the discretion of the investigator. If the infusion reaction is severe or prolonged, methylprednisolone 100 mg (or the equivalent) should be administered as well. For subsequent infusions in subjects who experience an infusion reaction and do not require discontinuation of MEDI-551 (see Section 6.4.1), acetaminophen and an antihistamine may be administered prior to initiation of the MEDI-551 infusion. If a subject experiences a Grade 3 infusion reaction, all subsequent administration of MEDI-551 must be preceded by IV methylprednisolone 100 mg (or the equivalent) 30 minutes prior to initiation of MEDI-551 infusion. Investigators may administer steroids during any cycle at their discretion as clinically indicated and per their institution's guidelines.

Arms B, C, and D

The use of the 2 dosage strengths, [REDACTED], will be specified by the sponsor. Subjects who begin therapy with the [REDACTED] form will continue therapy with that dosage form. Subjects in cohorts of Arms B, C and D receiving MEDI-551 at dose levels of 12 mg/kg or less will receive the [REDACTED] dosage form. However, the [REDACTED] ([REDACTED]) investigational product must be used for the 24 and 48 mg/kg cohorts of Arm B. The dose of MEDI-551 must be prepared using aseptic technique. MEDI-551 has been shown to be compatible with PVC-, DEHP-, and latex-free infusion bags containing a total volume of 250 mL of 0.9% sodium chloride for injection. An amount of 0.9 % sodium chloride equal to the volume of MEDI-551 solution to be added should be removed from the infusion bag, and then the calculated amount of MEDI-551 should be added to the infusion bag. The prepared solution may be stored at room temperature prior to being administered to the subject. MEDI-551 infusion must begin within 4 hours after preparation. If the infusion of the dose is not initiated within 4 hours, a new dose must be prepared using a new vial, as the MEDI-551 product contains no bacteriostatic agents. MEDI-551 will be administered by IV infusion using a 0.2-micron in-line filter.

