All subjects must receive mandatory premedication consisting of a minimum dose of 60 mg of IV methylprednisolone (or its equivalent) as well as 500 to 650 mg oral acetaminophen (or

paracetamol equivalent) and 50 mg IV diphenhydramine (or its equivalent) before the start of the initial MEDI-551 infusion. The initial infusion of MEDI-551 will be administered a minimum of 30 to 60 minutes after administration of mandatory premedications (as described in this section) according to the following sequence of infusion rates, regardless of dosage form:

- 1 mL/minute for a minimum of 15 minutes, then
- 2 mL/minute for a minimum of 15 minutes, then
- 4 mL/minute to complete the infusion

The minimum infusion time will be 81 minutes. Subjects receiving doses ≥ 24 mg/kg in Arm B will receive the initial infusion over 2 days on Day 1 and Day 2 of Cycle 1. The Day 1 infusion will be administered over a minimum of 81 minutes as described above. The Day 2 infusion will be administered over a minimum of 60 minutes (+ 15 minutes at the investigator's discretion). If the subject experiences an infusion reaction on Day 1, the Day 2 infusion will be administered over a minimum of 90 minutes. Subjects will be monitored closely during the initial infusion of MEDI-551, with vital signs recorded every 5 minutes over the first 30 minutes of the infusion and then every 15 minutes for the remainder of the infusion duration. Additional details regarding vital signs monitoring during the initial infusion of MEDI-551 are provided in Section 6.4.3. For subsequent infusions, MEDI-551 will be administered over 60 minutes (+ 15 minutes at the investigator's discretion). Vital signs will be monitored as described in Section 6.4.3. The initial infusion of MEDI-551 will be administered on Day 1 of Cycle 1 for Arms B and D, and Day 2 of Cycle 1 for Arm C.

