In the event of an IRR, the infusion of MEDI-551 may be interrupted until resolution of the event (up to 4 hours) and re-initiated at the 1-mL/minute rate. MEDI-551 infusion must be completed within 4 hours after the initial start of the infusion (NOTE: This is in addition to the 4 hours permitted from preparation of MEDI-551 solution to start of infusion). A new IP solution is required to be prepared if MEDI-551 infusion is not able to be completed within 4 hours after the initial start of the infusion. The rate may be increased slowly (by 50% every 15 minutes) until completion of the infusion. If the infusion reaction is severe or prolonged, methylprednisolone 100 mg (or the equivalent) may be administered in addition to acetaminophen (or institutional equivalent) and/or an antihistamine at the discretion of the investigator for management of the IRR ([Simons, 2010](#); [Sampson et al, 2006](#)). In the event of a Grade 4 IRR, MEDI-551 should be permanently discontinued (see Section 4.5.2.1 and Section 4.5.6).

If a subject experiences a Grade 3 IRR and does not require permanent discontinuation of MEDI-551 (see Section 4.5.2.1 and Section 4.5.6), all subsequent administration of MEDI-551 must be preceded by IV methylprednisolone 100 mg (or the equivalent), oral acetaminophen 500 to 650 mg (or equivalent dose of paracetamol), and IV diphenhydramine (or its equivalent) 50 mg 30 to 60 minutes prior to initiation of MEDI-551 infusion. Subjects who only experience a Grade 1 or 2 IRR and do not require permanent discontinuation of MEDI-551 (see Section 4.5.2.1) may receive methylprednisolone (or the equivalent), acetaminophen (or paracetamol equivalent), and diphenhydramine 30 to 60 minutes prior to initiation of the MEDI-551 infusion at the investigator's discretion.

As with any antibody, allergic reactions to dose administration are possible. Therefore, appropriate drugs and medical equipment to treat acute anaphylactic reactions must be immediately available, and study personnel must be trained to recognize and treat anaphylaxis.

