6.2 Assessment and Recording of Safety Parameters

6.2.1 Assessment of Severity

Assessment of severity is one of the responsibilities of the investigator in the evaluation of AEs and SAEs. The determination of severity should be made by the investigator based upon medical judgment and the severity categories of Grade 1 to 5 as generally defined below.

Grade 1	An event that is usually transient and may require only minimal treatment or therapeutic intervention. The event does not generally interfere with usual activities of daily living.
Grade 2	An event that is usually alleviated with additional specific therapeutic intervention. The event interferes with usual activities of daily living, causing discomfort but poses no significant or permanent risk of harm to the subject.
Grade 3	An event that requires intensive therapeutic intervention. The event interrupts usual activities of daily living, or significantly affects the clinical status of the subject. The event poses a significant risk of harm to the subject, and hospitalization may be required.
Grade 4	An event, and/or its immediate sequelae, that is associated with an imminent risk of death or is with physical or mental disabilities that affect or limit the ability of the subject to perform activities of daily living (eating, ambulation, toileting, etc).
Grade 5	The termination of life as a result of an event.

Severity will be graded according to the NCI CTCAE V4.03 ([CTCAE, 2010](#)).

It is important to distinguish between serious criteria and severity of an AE. Severity is a measure of intensity whereas seriousness is defined by the criteria in Section 6.1.2. A Grade 3 need not necessarily be considered an SAE. For example, a Grade 3 headache that persists for several hours may not meet the seriousness criteria and would be considered an AE, whereas a Grade 2 myocarditis requiring hospitalization for pain management would be considered an SAE.

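### For a Grade 3 infusion reaction in Arms B, C and D, the dose-modification table and Sections 4.5.3, 6.4.1 and 6.4.3 give conflicting instructions on steroid, interruption and restart

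*Protocol*

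**What the plan says.** Four places in the current protocol body deal with a Grade 3 infusion reaction in Arms B, C and D.

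- **Table 4.5.2.1-2**, nonhematologic toxicity, Grade 3 or 4, first occurrence: "For Grade 3 infusion reaction, infusion must be stopped for up to 4 hours until the subject recovers". It continues: "An additional dose of steroids will be given and the infusion may resume", at half the rate for the rest of the infusion. If the reaction does not respond to medical therapy, "or that occurs despite steroid prophylaxis, discontinue MEDI-551".
- **Section 4.5.3**, text for Arms B, C and D: "If the infusion reaction is severe or prolonged, methylprednisolone 100 mg (or the equivalent) may be administered in addition to acetaminophen" and/or an antihistamine, at the investigator's discretion. The infusion may be interrupted and restarted at 1 mL/minute, with gradual increases.
- **Section 6.4.3**, text for Arms B, C and D: the same permission and the same restart rule.
- **Section 6.4.1**: dosing may be interrupted for up to 4 hours for Grade 2 or 3 reactions. Item 3 adds that Grade 3 reactions of limited duration that respond to treatment or to a slower rate need neither interruption nor discontinuation.

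Section 4.5.3 also sets premedication before the first MEDI-551 infusion: "All subjects must receive mandatory premedication consisting of a minimum dose of 60 mg of IV methylprednisolone (or its equivalent"), with acetaminophen and diphenhydramine.

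**The concern.** Section 1.6 names infusion reactions as the identified risk of MEDI-551, so the handling of a Grade 3 reaction should read the same wherever a site looks it up. It does not. A site working from the administration section can restart an infusion without the steroid that the table requires, and still be following the protocol as written there.

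Two later rules depend on how a reaction was handled. Permanent discontinuation turns partly on whether it responded to medical therapy (Table 4.5.2.1-2, Section 6.4.1). In Arms B and C, one exemption from the definition of a dose-limiting toxicity turns on resolution within 6 hours under appropriate management (Section 4.5.6). If the required management differs by page, those judgements could in principle differ too.

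**Working it through.** No sample size, power or event count is involved. The check is a comparison of the texts, with one small calculation on the restart rate.

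1. **Steroid.** The table makes it a requirement; Sections 4.5.3 and 6.4.3 make it a permission. The sections use *severe or prolonged* as the trigger, not a grade. Section 6.2.1 says "Severity will be graded according to the NCI CTCAE V4.03" but does not equate *severe* with Grade 3. The conflict survives either reading. If Grade 3 counts as severe, the sections make the steroid optional; if it does not, they do not call for it at all.

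2. **Precedence.** Section 4.5.2.1 sends Grade 2 to 4 events to the table but does not say that the table overrides other text. Sections 4.5.3 and 6.4.3 point back to 4.5.2.1 only on permanent discontinuation. What they make mandatory after a Grade 3 reaction is steroid premedication before later infusions, which is a different step. Sections 4.5.4 and 6.4.1 do not settle the matter.

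3. **Interruption.** Required (table), permitted (4.5.3 and 6.4.3), and not necessary for responsive reactions of limited duration (6.4.1, item 3).

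4. **Restart rate.** Assume the 250 mL bag of Section 4.5.3. It fits the protocol's own minimum time for the first infusion: 15 min × 1 mL/min + 15 min × 2 mL/min = 45 mL, then (250 − 45) / 4 = 51.25 min, and 30 + 51.25 = 81.25 min against the stated 81.
   - Later infusions run over 60 to 75 minutes: 250/60 = 4.17 mL/min, or 250/75 = 3.33 mL/min.
   - Table: half of that for the remainder, 2.08 or 1.67 mL/min.
   - Sections 4.5.3 and 6.4.3: restart at 1 mL/min. If every 50% step is taken, the rate after 15, 30 and 45 minutes is 1.5, 2.25 and 3.38 mL/min if the steps compound, or 1.5, 2.0 and 2.5 mL/min if each adds 50% of the restart rate.
   - The sections therefore start slower than the table and, by 45 minutes at the latest, can run faster.

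5. **Reach.** Premedication is mandatory at the first infusion, and a Grade 3 reaction despite prophylaxis ends treatment. After one Grade 3 reaction, all later infusions need steroid premedication. The steroid-then-resume route is thus left mainly for a first Grade 3 reaction at a later, unpremedicated infusion. The table's reference to an *additional* dose fits that case poorly, because it implies an earlier one.

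6. **Numbers exposed.** Section 3.1 gives 9 subjects on treatment across the whole study on 19Jan2017, so between 0 and 9 were in Arms B to D. For past dose-limiting toxicities, Section 7.5 gives 7 escalation subjects in Arm B and 3 + 3 = 6 in Arm C, 13 in all. Section 4.5.6 does not apply to Arm D.

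**The case against.** The best defence is that the texts describe different things. The table's dose can be read as given after recovery, as a condition of restarting, while Sections 4.5.3 and 6.4.3 concern acute treatment. On that reading the table's dose could not affect whether the reaction resolved. A second defence is that the table is the specific rule and the sections are general: a site that gives the steroid satisfies both.

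Both readings are possible, but the protocol states neither. Sections 4.5.3 and 6.4.3 set out a full sequence of interruption, resolution and restart, with no steroid required before restart. A site following them can omit what the table demands. Nor does obeying both work for the restart rate, where half rate to the end and 1 mL/minute with increases are different instructions.

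The objection to the consequences largely stands. A reader might infer that discontinuations and dose-limiting toxicity counts in these arms depended on which page a site read. The documents do not support that. A Grade 3 reaction despite prophylaxis leads to discontinuation whatever is given afterwards. The 6-hour exemption covers only a first occurrence without steroid prophylaxis, so on its terms it excludes the premedicated first infusion. Section 15 reports Grade 3 reactions in 2 of 3 subjects at 6 mg/kg in Arm B, but at the first infusion. That shows the event is real, not that this route was used.

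It is also fair that escalation is finished, so a clarification cannot change past classifications.

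**Conclusion.** The contradiction holds as one of wording, on three steps: whether a steroid is required, whether the infusion has to be stopped, and how it restarts. It should be corrected, because it concerns the drug's identified risk and the text still governs any Arm B to D subjects being infused.

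The practical size is small. It mainly touches a first Grade 3 reaction at a later infusion without steroid prophylaxis, in at most the 9 subjects on treatment at the stated date. For past dose-limiting toxicities, 13 escalation subjects is a ceiling on exposure, not an estimate of effect; only their Cycle 1 infusions after the first are in question. The protocol gives no count of such reactions, so neither the share of reactions treated with steroid nor any effect on results can be derived.

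A reader might also take Arm A's firmer steroid wording as part of the conflict. It is not: Arm A has its own premedication and infusion rules, and different arms may differ.

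The conclusion assumes that a Grade 3 reaction falls within the scope of Sections 4.5.3 and 6.4.3, which do not exclude it. The rate comparison assumes a 250 mL infusion.

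**What to change.** Reconcile Table 4.5.2.1-2 with Sections 4.5.3, 6.4.1 and 6.4.3 into one statement on Grade 3 infusion reactions in Arms B, C and D. It should say whether the steroid is required or discretionary, and give one instruction each for interruption and restart. If a steroid is named in more than one place, agent and dose should agree. The other sections should then cross-refer to that statement. The table's mention of an additional dose should be squared with its own rule on reactions despite prophylaxis. Which rule applies is a clinical decision for the sponsor. The cost is a protocol text clarification, with no change to design or analysis.

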4.5.3 Investigational Product Preparation and Administration

The day of receipt of the first dose of investigational product is considered Day 1. The weight used to calculate the dose will be the weight on Day 1 of each cycle. The weight at screening may be used for Cycle 1, Day 1 if the weight on Day 1 is within 10% of the screening weight. No change in dose should be made during a particular cycle unless a change in weight of greater than 10% is observed from the weight used to calculate the dose for that cycle. An equation for weight-based dose calculation is provided below.

$$\text{Drug Volume (mL)} = \text{Dose (mg/kg)} \times \text{Patient Weight (kg)} \div \text{Product Concentration (mg/mL)}$$

The dose of investigational product for administration must be prepared by the investigators or site’s designated investigational product manager using aseptic technique. The investigational product manager will select the appropriate number of vials of investigational product required to prepare the subject’s dose. Allow the vial(s) to come to room temperature.

To prepare investigational product for administration, the investigational product manager should remove the tab portion of the vial cap and clean the rubber stopper with 70% ethyl alcohol or equivalent. To avoid foaming, the vial should not be shaken. A vial should only be used one time to prepare a single dose.

Arm A

The dose of MEDI-551 must be prepared using aseptic technique. MEDI-551 must be diluted for IV administration in a PVC-, DEHP-, and latex-free infusion bag containing a total volume of 250 mL of 0.9% sodium chloride for injection. An amount of 0.9 % sodium chloride equal to the volume of MEDI-551 solution to be added should be removed from the infusion bag, and then the calculated amount of MEDI-551 should be added to the infusion bag. The prepared solution may be stored at room temperature prior to being administered to the subject. MEDI-551 must be administered within 8 hours after preparation. If the dose is not administered within 8 hours, a new dose must be prepared using a new vial, as the MEDI-551 product contains no bacteriostatic agents.

MEDI-551 will be administered as an IV infusion over 60 minutes (+ 15 minutes) using a 0.2 micron filter. Subjects will be monitored during and after infusion with assessment of vital signs every 15 minutes during infusion, at the end of infusion, and 30 and 60 minutes after the infusion.

In the event of an IRR, the infusion of MEDI-551 may be decreased by 50% or interrupted until resolution of the event (up to 4 hours) and re-initiated at 50% of the initial rate until completion of the infusion. Acetaminophen and/or an antihistamine (eg, diphenhydramine) may be administered at the discretion of the investigator. If the infusion reaction is severe or prolonged, methylprednisolone 100 mg (or the equivalent) should be administered as well. For subsequent infusions in subjects who experience an infusion reaction and do not require discontinuation of MEDI-551 (see Section 6.4.1), acetaminophen and an antihistamine may be administered prior to initiation of the MEDI-551 infusion. If a subject experiences a Grade 3 infusion reaction, all subsequent administration of MEDI-551 must be preceded by IV methylprednisolone 100 mg (or the equivalent) 30 minutes prior to initiation of MEDI-551 infusion. Investigators may administer steroids during any cycle at their discretion as clinically indicated and per their institution's guidelines.

Arms B, C, and D

The use of the 2 dosage strengths, [REDACTED], will be specified by the sponsor. Subjects who begin therapy with the [REDACTED] form will continue therapy with that dosage form. Subjects in cohorts of Arms B, C and D receiving MEDI-551 at dose levels of 12 mg/kg or less will receive the [REDACTED] dosage form. However, the [REDACTED] ([REDACTED]) investigational product must be used for the 24 and 48 mg/kg cohorts of Arm B. The dose of MEDI-551 must be prepared using aseptic technique. MEDI-551 has been shown to be compatible with PVC-, DEHP-, and latex-free infusion bags containing a total volume of 250 mL of 0.9% sodium chloride for injection. An amount of 0.9 % sodium chloride equal to the volume of MEDI-551 solution to be added should be removed from the infusion bag, and then the calculated amount of MEDI-551 should be added to the infusion bag. The prepared solution may be stored at room temperature prior to being administered to the subject. MEDI-551 infusion must begin within 4 hours after preparation. If the infusion of the dose is not initiated within 4 hours, a new dose must be prepared using a new vial, as the MEDI-551 product contains no bacteriostatic agents. MEDI-551 will be administered by IV infusion using a 0.2-micron in-line filter.

All subjects must receive mandatory premedication consisting of a minimum dose of 60 mg of IV methylprednisolone (or its equivalent) as well as 500 to 650 mg oral acetaminophen (or

paracetamol equivalent) and 50 mg IV diphenhydramine (or its equivalent) before the start of the initial MEDI-551 infusion. The initial infusion of MEDI-551 will be administered a minimum of 30 to 60 minutes after administration of mandatory premedications (as described in this section) according to the following sequence of infusion rates, regardless of dosage form:

- 1 mL/minute for a minimum of 15 minutes, then
- 2 mL/minute for a minimum of 15 minutes, then
- 4 mL/minute to complete the infusion

The minimum infusion time will be 81 minutes. Subjects receiving doses ≥ 24 mg/kg in Arm B will receive the initial infusion over 2 days on Day 1 and Day 2 of Cycle 1. The Day 1 infusion will be administered over a minimum of 81 minutes as described above. The Day 2 infusion will be administered over a minimum of 60 minutes (+ 15 minutes at the investigator's discretion). If the subject experiences an infusion reaction on Day 1, the Day 2 infusion will be administered over a minimum of 90 minutes. Subjects will be monitored closely during the initial infusion of MEDI-551, with vital signs recorded every 5 minutes over the first 30 minutes of the infusion and then every 15 minutes for the remainder of the infusion duration. Additional details regarding vital signs monitoring during the initial infusion of MEDI-551 are provided in Section 6.4.3. For subsequent infusions, MEDI-551 will be administered over 60 minutes (+ 15 minutes at the investigator's discretion). Vital signs will be monitored as described in Section 6.4.3. The initial infusion of MEDI-551 will be administered on Day 1 of Cycle 1 for Arms B and D, and Day 2 of Cycle 1 for Arm C.

In the event of an IRR, the infusion of MEDI-551 may be interrupted until resolution of the event (up to 4 hours) and re-initiated at the 1-mL/minute rate. MEDI-551 infusion must be completed within 4 hours after the initial start of the infusion (NOTE: This is in addition to the 4 hours permitted from preparation of MEDI-551 solution to start of infusion). A new IP solution is required to be prepared if MEDI-551 infusion is not able to be completed within 4 hours after the initial start of the infusion. The rate may be increased slowly (by 50% every 15 minutes) until completion of the infusion. If the infusion reaction is severe or prolonged, methylprednisolone 100 mg (or the equivalent) may be administered in addition to acetaminophen (or institutional equivalent) and/or an antihistamine at the discretion of the investigator for management of the IRR ([Simons, 2010](#); [Sampson et al, 2006](#)). In the event of a Grade 4 IRR, MEDI-551 should be permanently discontinued (see Section 4.5.2.1 and Section 4.5.6).

If a subject experiences a Grade 3 IRR and does not require permanent discontinuation of MEDI-551 (see Section 4.5.2.1 and Section 4.5.6), all subsequent administration of MEDI-551 must be preceded by IV methylprednisolone 100 mg (or the equivalent), oral acetaminophen 500 to 650 mg (or equivalent dose of paracetamol), and IV diphenhydramine (or its equivalent) 50 mg 30 to 60 minutes prior to initiation of MEDI-551 infusion. Subjects who only experience a Grade 1 or 2 IRR and do not require permanent discontinuation of MEDI-551 (see Section 4.5.2.1) may receive methylprednisolone (or the equivalent), acetaminophen (or paracetamol equivalent), and diphenhydramine 30 to 60 minutes prior to initiation of the MEDI-551 infusion at the investigator's discretion.

As with any antibody, allergic reactions to dose administration are possible. Therefore, appropriate drugs and medical equipment to treat acute anaphylactic reactions must be immediately available, and study personnel must be trained to recognize and treat anaphylaxis.

For Arm C only: Rituximab will be administered per institutional guidelines (see [Appendix 2](#) for rituximab prescribing information). All subjects must receive mandatory premedication consisting of a minimum dose of 60 mg IV methylprednisolone (or its equivalent) as well as 500 to 650 mg oral acetaminophen (or paracetamol equivalent), and 50 mg IV diphenhydramine 30 to 60 minutes before the start of the initial rituximab infusion on Day 1 of Cycle 1. The initial infusion of rituximab will be administered over a minimum of 30 to 60 minutes after administration of mandatory premedications. On Day 2 of Cycle 1, MEDI-551 will be administered over a minimum of 81 minutes following mandatory premedications as indicated above under "Arms B, C, and D". On Day 8 of Cycle 1 and Day 1 of Cycle 2, MEDI-551 should be administered first with rituximab administration a minimum of 30 minutes after completion of the MEDI-551 infusion.

